## Chapter 3: Study Follow-up

419

### 3.1 Study Follow-up Visits

420

Participants randomized in the study generally\* will return for follow-up according to the following schedule (timed from randomization, unless otherwise specified):

422

Protocol-specified Visit/Call	Target Day	Target Window (around target day)	Allowable Window (around target day)
1-month call	Randomization+30 days	± 1 week 23 to 37 days	1 to 76 days
3-month visit	Randomization+91 days	± 2 weeks 77 to 105 days	± 1.5 months 46 to 137 days
6-month visit	Randomization+183 days	± 2 weeks 169 to 197 days	± 1.5 months 138 to 228 days
9-month visit	Randomization+274 days	± 2 weeks 260 to 288 days	± 1.5 months 229 to 320 days
12-month visit	Randomization+365 days	± 2 weeks 351 to 379 days	-1.5 to +3 months 321 to 457 days
18-month visit	Randomization+548 days	± 2 weeks 534 to 562 days	± 3 months 458 to 639 days
24-month visit	Randomization+731 days	± 2 weeks 717 to 745 days	± 3 months 640 to 822 days
30-month visit	Randomization+913 days	± 2 weeks 899 to 927 days	± 3 months 823 to 1004 days
36-month Primary Outcome Visit b	Randomization+1096 days	± 2 weeks 1068 to 1124 days	-3 to +6 months 1005 to 1278 days
38-month Secondary Outcome Visit c,d	36-month visit +60 days (or 38-months from randomization for confirmed failures occurring before 36 months).	± 4 weeks 32 to 88 days	-1 month to +6.5 months 30 to 258 days from 36-month Visit (from 38 months following randomization for confirmed failures)
Additional if needed	Target Day	Target Window (around target day)	Allowable Window (around target day)
1-month call after new spectacles e	Visit at which spectacles changed +30 days	± 1 week 23 to 37 days	1 to 76 days
Failure Confirmation Visit f	Visit at which failure criteria met and spectacles updated + 60 days	± 4 weeks 46 to 88 days	30 days to open end (must be completed)
Post-failure Secondary Outcome Visit g	Visit at which failure confirmed +60 days	± 4 weeks 32 to 88 days	-1 month to +6.5 months 30 to 258 days from confirmed failure

b SVL group is prescribed BFLs at end of the 36-month Primary Outcome Visit. The exception is participants who previously failed, had the post-failure secondary outcome visit, and been released to treatment.

c Note that participants who meet failure criteria at 36 months (and have not failed previously) and need their spectacles updated will have a Failure Confirmation Visit 2 months later (4-12 weeks) and return at 40 months for the 38-month Secondary Outcome Visit.

d At the 38-month Secondary Outcome Visit, both groups are now in BFLs.

e Phone calls from site 1 month  $\pm$  1 week from the time spectacles are prescribed or changed (section 3.1.1).

fFailure Confirmation Visit: If a participant meets failure criteria at the 12-month visit or later and needs a change in refractive correction, new spectacles will be prescribed, and the participant will return in 4 to 12 weeks to determine (confirm) whether the participant meets failure criteria.

g Post-failure Secondary Outcome Visit: If a participant meets failure criteria prior to 36 months, BFLs will be prescribed to the SVL group (BFLs continued in the BFL group) and a Post-failure Secondary Outcome Visit will be scheduled 4 to 12 weeks after the visit at which failure criteria was confirmed (i.e., at a regularly-scheduled study visit or at a separate Failure Confirmation Visit, if one is required).

\*Participants who meet confirmed failure criteria (section 3.5) and complete the Post-failure Secondary Outcome Exam will return for the 12- and 24-month follow-up visits (if they have not already been completed) and the 38-month Secondary Outcome Visit as outlined in section 3.7.1; all other remaining visits will be skipped.

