## JAEB CENTER FOR HEALTH RESEARCH

TF + 3.00 = trial frames with current refractive correction worn at enrollment (or plano, if emmetropia) with +3.00 D. The two sphere powers should be added and a single lens used for the spherical power component of the trial frames.

BFLtop = participant viewing through top portion of bifocal lenses (looking over BFL segment)

BFLbot = participant viewing through the BFL segment situated at the bottom of the lenses

Home = randomized spectacles worn full-time when not in the office

Hometop = randomized spectacles worn full-time when not in the office with participant viewing through top (distance) portion with bottom half taped (for masking)

ME = masked examiner

Office = SVLs comprised of cycloplegic refraction with +3.00 D added (to be kept at clinic for testing)

a Visual acuity can be completed at the end of the visit, if desired.

b Prescribe assigned spectacles per randomization (BFLs or SVLs)

c Participants with confirmed failure prior to the 36-month Primary Outcome visit and completing their Post-failure Secondary Outcome Visit will only return for interim follow-up visits at 12 and 24 months with abbreviated testing (monocular distance VA, near stereoaucuity, and ocular alignment).

d Additional testing is completed if a failure criterion is met prior to the 36-month visit (and failure has not been met and confirmed at a prior visit). Additional testing must be done prior to the cycloplegic refraction.

e At the 36-month visit, prescribe BFLs for participants randomized to the SVL group; continue BFLs for those randomized to the BFL group. The exceptions are: 1) participants who met confirmed failure criteria at a previous visit, who underwent 2 months of BFL spectacle wear and the Post-Failure Secondary Outcome Visit, and who now continue with treatment (or no treatment) at investigator discretion; and 2) participants who have unconfirmed failure at 36 months, who have their randomized treatment spectacles updated and return to have failure confirmed/not confirmed at the Failure Confirmation Visit.

f 36-month Primary Outcome Visit not required for participants with previously confirmed failure.

g For visits prior to 36 months:

- If failure NOT CONFIRMED, continue current randomized spectacle correction

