### 583 **3.4.1 Prescribing Bifocal Spectacles at the 36-month Primary Outcome Visit**

584 For participants who HAVE NOT failed prior to or by the end of the 36-month Primary Outcome  
585 Visit:

- 586     • Participants in the SVL group will be prescribed BFLs to be worn until the 38-month  
587 Secondary Outcome Visit.
- 588     • Participants in the BVL group will continue to wear BFLs until the 38-month Secondary  
589 Outcome Visit.

590  
591 For participants who FAIL AT the 36-month Primary Outcome Visit:

- 592 • SVL participants who meet CONFIRMED failure criteria at the 36-month visit (i.e., fail  
593 and do not require a change in spectacles) will be prescribed BFLs to be worn until the  
594 38-month Secondary Outcome Visit.
- 595 • BFL participants who meet CONFIRMED failure criteria at the 36-month visit (i.e., fail  
596 and do not require a change in spectacles) will continue to wear their BFLs until the 38-  
597 month Secondary Outcome Visit.
- 598 • Participants in both treatment groups who meet failure criteria at the 36-month visit and  
599 require a Failure Confirmation Visit (see section 3.6) because their spectacles are NOT  
600 within study tolerance will be prescribed updated spectacles according to their respective  
601 treatment group and return for a Failure Confirmation Visit.

602 BFL spectacles that are being prescribed per protocol at the 36-month Primary Outcome Visit (as  
603 opposed to being prescribed at investigator discretion) should meet the following criteria based  
604 on the participant's most recent cycloplegic refraction:

- 607 • Full correction of hyperopia/myopia
- 608 • Full correction of astigmatism
- 609 • Full correction of anisometropia
- 610 • +3.00 D bifocal add (flat top, 35 mm, segment height set mid-pupil, see *ETS3 Manual of*  
611 *Procedures*).
- 612 • Children with no refractive error (emmetropia or plano refraction) will be prescribed  
613 spectacles with plano lenses and the +3.00 D bifocal add.

614 Progressive addition lenses (PALs) are NOT allowed during the study. SVL participants will  
615 wear their newly prescribed BFL spectacles until their 38-month Secondary Outcome Visit.

617 Regardless of the correction worn, all participants return for the 38-month Secondary Outcome  
618 Visit.

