### 691       **3.5.2 Procedures for Participants Meeting Failure Criteria AT the 36-month Primary 692           Outcome Visit**

693       All participants who meet failure criteria AT the 36-month visit must have a cycloplegic  
694       refraction at the end of this study visit (after eye alignment, stereoacuity, and other binocular  
695       function testing, etc.):

- 696       • The cycloplegic refraction must be performed 30 to 45 minutes following at least  
697       one application of cyclopentolate 1%.
- 698       • If cycloplegic refraction reveals that the spectacles are no longer within the  
699       spectacle tolerance criteria according to section 3.12, then both HOME and  
700       OFFICE spectacle corrections must be updated.

701

702       **NOTE:** All eye alignment, stereoacuity, and other binocular function testing must  
703       already have been completed as part of the 36-month Primary Outcome visit (for all  
704       participants) before instilling cyclopentolate drops.

705

706       If the spectacle correction IS within tolerance (section 3.12) and does not need to be updated:

- 707           1. Failure is CONFIRMED at this 36-month visit.
- 708           2. SVL group participants should be prescribed BFLs and BFL group participants continued  
709           in BFLs (section 3.4.1)
- 710           3. Both groups should return in 2 months (window: 4 to 12 weeks) for their 38-month  
711           Secondary Outcome Visit (section 3.8).

- 712  
713 If the spectacle correction is NOT within tolerance (section 3.12) and needs to be updated:  
714 1. Failure is NOT CONFIRMED at this 36-month visit.  
715 2. Participants should be prescribed new spectacles (according to the criteria in section 2.8)  
716 consistent with their randomized group assignment.  
717 3. Participants should return for a Failure Confirmation Visit in 2 months (window: 4 weeks  
718 to 12 weeks).  
719 4. Regardless of whether study failure criteria are confirmed or not confirmed at the Failure  
720 Confirmation Visit, all SVL participants will be prescribed BFLs and all BFL participants  
721 will continue with BFL wear (section 3.4.1).  
722 5. Both groups return in 2 months (window: 4 to 12 weeks) following the Failure  
723 Confirmation Visit for their 38-month Secondary Outcome Visit. In this specific  
724 situation, the 38-month Secondary Outcome Visit will be scheduled at 40 months after  
725 randomization (section 3.8).

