726 **3.6 Failure Confirmation Visit**

727 Failure Confirmation Visits occur 2 months (window: 4 to 12 weeks) after suspected failures that  
728 occurred for participants who were found to need a change in spectacles at that time. The  
729 purpose of the Failure Confirmation Visit is to determine whether failure criteria are met after  
730 the participant has been wearing the updated randomized treatment spectacles. Note that meeting  
731 *any* failure criteria in updated spectacles will be considered a CONFIRMED failure. It is not  
732 required that the participant fail the same criterion that was initially failed before the spectacles  
733 were updated (e.g., could have failed distance motor criterion initially but now fails near stereo  
734 criterion; this is still failure).

735 **NOTE:** The Failure Confirmation Visit (if required) is not allowed to be missed regardless of  
736 timing. If the timing of the Failure Confirmation Visit overlaps with a subsequent follow-up  
737 visit, the Failure Confirmation Visit must be completed *in lieu of* the follow-up visit (or  
738 *before* the 38-month visit). Regardless of whether any regularly scheduled follow-up visits  
739 have been missed, the Failure Confirmation Visit must be completed when the participant  
740 returns at the next study visit.

741 All testing in section 3.4 (same as 36-month Primary Outcome Visit) must be repeated at the  
742 Failure Confirmation Visit, with participants wearing their HOME spectacles or OFFICE  
743 spectacles (or appropriate trial frames) as specified.

- 744 • If failure criteria are NOT CONFIRMED at a Failure Confirmation Visit occurring  
745 before the 36-month visit, no changes are made to treatment and the participant  
746 continues with the next scheduled follow-up visit for which the participant is not  
747 currently in the window, regardless of how soon.
- 748  
749 • If failure criteria are NOT CONFIRMED at a Failure Confirmation Visit occurring after  
750 the 36-month Primary Outcome Visit, participants will:  
751     ○ Be prescribed BFLs (if in SVL group) or continued in BFLs (if in the BFL group)  
752         (section 3.4.1)  
753     ○ Return in 2 months (window: 4 to 12 weeks) for their 38-month Secondary  
754         Outcome Visit (section 3.8).

- 756     • If failure criteria are CONFIRMED at **ANY** Failure Confirmation Visit (regardless of  
757        timing), participants will:  

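### Footnote b of the visit table omits the unconfirmed 36-month failure and so conflicts with the sections that retest that child in randomized lenses before any bifocal prescription

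*Protocol*

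**What the plan says.** Footnote b is attached to the 36-month row of the visit table in section 3.1. It reads "SVL group is prescribed BFLs at end of the 36-month Primary Outcome Visit" and continues "The exception is participants who previously failed, had the post-failure secondary outcome visit, and been released to treatment". It names no other exception.

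Footnote e of the Schedule of Study Visits and Procedures covers the same prescribing decision and lists two exceptions. The first matches footnote b. The second is "participants who have unconfirmed failure at 36 months, who have their randomized treatment spectacles updated and return to have failure confirmed/not confirmed".

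Section 3.4.1 agrees with footnote e. Children in either group who meet failure criteria at 36 months and whose spectacles are not "within study tolerance will be prescribed updated spectacles according to their respective" treatment group, and they return for a Failure Confirmation Visit.

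Section 3.5.2 gives the order. New spectacles are prescribed "consistent with their randomized group assignment", the confirmation visit follows, and item 4 then states that, whatever the result of the "Confirmation Visit, all SVL participants will be prescribed BFLs and all BFL participants" continue in theirs. Section 3.6 gives the purpose of that visit: to see whether failure criteria are met after "the participant has been wearing the updated randomized treatment spectacles".

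**The concern.** Under section 7.6, a child counts as a failure from the visit at which failure is confirmed, so the Failure Confirmation Visit fixes both primary-outcome status and event time. For a child first failing at 36 months with spectacles out of tolerance, the protocol gives two different instructions about the lens worn until that visit. The difference bites in one group only. A BFL child wears bifocals under either instruction, whereas an SVL child wears single-vision lenses under one and bifocals under the other. If some sites followed footnote b, confirmation in the SVL group would not be the confirmation that section 3.6 defines.

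**Working it through.** No stated figure is involved, so there is nothing to recompute. The check takes one child through each passage: randomized to SVL, no earlier confirmed failure, first meets a failure criterion at the 36-month visit, and the cycloplegic refraction that day shows the spectacles out of tolerance.

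1. **Section 3.1, footnote b.** The sole exception requires an earlier failure, a completed post-failure visit and release to treatment. This child has none of these, so the general rule applies: bifocals at the end of the 36-month visit.
2. **Schedule footnote e.** The second exception applies: randomized spectacles are updated and the child returns for confirmation.
3. **Section 3.4.1.** Updated spectacles according to treatment group, then the Failure Confirmation Visit.
4. **Section 3.5.2, items 2 to 4.** New spectacles of the randomized type, confirmation visit, then bifocals.
5. **Section 3.6.** Failure is judged after wear of updated randomized spectacles.
6. **Section 3.1, footnotes c and f, and the Failure Confirmation Visit row.** These show that the confirmation pathway exists and give its timing. They do not say which type of lens is worn, so they do not supply the missing exception.
7. **Schedule footnote g.** On the line for prescribing spectacles it is marked in the Failure Confirmation Visit column. Read there, its instruction to give bifocals whether or not failure is confirmed matches section 3.5.2, item 4. But it is worded as applying to the 36-month visit, so on its own it can be misread in the same way as footnote b.

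Steps 2 to 5 agree with each other, and step 1 contradicts them.

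Next, what bifocal wear could change at the confirmation visit, which repeats the section 3.4 tests:

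- **Near stereoacuity.** Section 3.5 uses the better of two tests in OFFICE spectacles, which carry +3.00 D over the distance correction in both groups (section 2.8). The test-day optics are the same whichever lens was worn at home.
- **Distance alignment.** It is measured through the top of the HOME lenses with the lower half taped. That is the distance correction in both groups.
- **Diplopia.** It is a parental report covering the last week, so it can reflect the lens worn at home.

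What remains is any carry-over into the first two tests from about 2 months of wear (window 4 to 12 weeks), and the diplopia report.

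Finally, who is affected. Three conditions must hold together: SVL group, first failure at 36 months, and spectacles out of tolerance. Children without confirmed failure have a scheduled refraction at 30 months with mandatory updating (section 3.3), so normally about 36 − 30 = 6 months of refractive change is at issue. The protocol gives no proportion for spectacles out of tolerance at that point.

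**The case against.** The best defence is that the operative text is settled. Sections 3.4.1, 3.5.2 and 3.6 and schedule footnote e all say the same thing. A site learns of the required refraction and tolerance check from section 3.5.2, which states the lens assignment in the same list, so the error needs someone to follow half of that section. This stands as far as it goes: the design is not unsettled, and the fault is an incomplete footnote. It does not remove the fault. Footnote b is a flat prescribing instruction with an explicit single exception, placed in the table that sets the visit schedule.

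Four stronger readings are tempting, and the document does not support them:

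- **That SVL failure status would simply be decided under the other group's treatment, lowering SVL failures.** The identical test optics rule this out for the stereoacuity and distance alignment measurements themselves. Fewer SVL failures is a plausible direction, but the protocol gives no estimate of carry-over or of the effect on diplopia reports.
- **That the synopsis contradicts section 3.5.2 as well.** It places the bifocal prescription after the 36-month visit. That fits section 3.5.2, where these children also receive bifocals after that visit, once retested. Leaving a sub-branch out of a synopsis is not a contradiction.
- **That the loss can be stated as a share of SVL events.** This would need the proportion with spectacles out of tolerance at 36 months, the proportion of sites following footnote b, and the chance that a child's status flips. The protocol gives none of these.
- **That section 7.6.1 must change.** Its suspected-failure analysis is for children lost before confirmation, and its crossover analysis is for switches before any clinical failure measure is met. A child switched under footnote b and then retested falls under neither. Counting retested children who did not fail as failures would nevertheless redefine the analysis. That is a preference and does not follow from the conflict.

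**Conclusion.** The conflict is real and sits on a step that decides the primary outcome. Footnote b, taken literally, sends an SVL child with an unconfirmed 36-month failure into bifocals before the retest. Footnote e and sections 3.4.1, 3.5.2 and 3.6 do not. Footnote g's wording is open to the same misreading. Any effect falls on the SVL group only and is limited to carry-over from bifocal wear and parent-reported diplopia. The number of children is probably very small, but this is a judgement from the three joint conditions and the 30-month refraction, because the protocol does not give it. There is an effect only if some sites act on footnote b in place of the detailed sections. The sample size and the planned analysis are untouched. The point deserves correction because it bears on the primary outcome and costs almost nothing to settle. No view is taken here on which lens rule is clinically right.

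**What to change.** Reconcile footnote b of the section 3.1 visit table, and the wording of schedule footnote g, with schedule footnote e and sections 3.4.1, 3.5.2 and 3.6, so that one rule governs the child with an unconfirmed failure at 36 months. In footnote g, make clear at which visit the instruction applies.

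For as long as sections 3.5.2 and 3.6 stand as written, list any SVL child given bifocals before a required Failure Confirmation Visit among the protocol deviations that section 7.11 already tabulates by treatment group. The number affected will then be known.

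The cost is two footnotes and one line in an existing tabulation. No analysis, sample size or visit changes.

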If treatment failure occurs, proceed according to whether the participant failed **PRIOR** to the 36-month Primary Outcome Visit (section 3.5.1) or **AT** the 36-month Primary Outcome Visit (section 3.5.2).

If failure has been **CONFIRMED** previously in the study, there is no need to confirm failure at subsequent visits. Participants with previously **CONFIRMED** failure will continue in follow-up as outlined in section 3.7.1 regardless of whether they meet failure criteria again on subsequent visits.

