### **3.5.1 Procedures for Participants Meeting Failure Criteria at a Study Visit **PRIOR** to the 36-month Primary Outcome Visit**

All participants who meet failure criteria **PRIOR** to the 36-month Primary Outcome Visit will undergo the following **additional** testing in the order specified below (1-5) at the visit when the failure criterion is met:

1. Random Dot Stereo Butterfly test (**masked**): tested in OFFICE spectacles at 33 cm.\*
2. Preschool Worth 4-Shape test (**masked**): tested in OFFICE spectacles at 33 cm.\*
3. Distance Randot Stereotest (**masked**): tested through **TOP** of HOME spectacles at 3 meters (with bottom half of lenses taped). (See *ETS3 Procedures Manual* for taping instructions)
4. Randot Preschool Stereoacuity Test (**masked**): tested through **TOP** of HOME spectacles at 33 cm (with bottom half of lenses taped) (See *ETS3 Procedures Manual*)\*
5. Cycloplegic Refraction (after the testing above is completed)

- 668     • The cycloplegic refraction must be performed 30 to 45 minutes following at least  
669       one application of cyclopentolate 1%.
- 670     • If the cycloplegic refraction reveals that the spectacles no longer meet the spectacle  
671       tolerance criteria according to section 3.12, the spectacle correction must be  
672       updated (both HOME and OFFICE spectacles).

673       \*Test distance for near stereoacuity and other binocular testing is 33 cm rather than 40 cm because of the focal  
674       length of the +3.00 D add.

675       If based on the cycloplegic refraction performed at this visit:

- 676       • The spectacle correction IS within tolerance (section 3.12) and does not need to be  
677       updated:
- 678           1. Failure is CONFIRMED at this visit.
  - 679           2. The participant should be prescribed BFLs (if in the SVL group) or continued in  
680           BFLs (if in the BFL group) (section 2.8)
  - 681           3. The participant should return in 2 months (window: 4 to 12 weeks) for their Post-  
682           failure Secondary Outcome Visit (section 3.7).
- 683
- 684       • The spectacle correction is NOT within tolerance (section 3.12) and needs to be updated:
- 685           1. Failure is NOT CONFIRMED at this visit.
  - 686           2. The participant should be prescribed new spectacles (according to the criteria in  
687           section 2.8) consistent with the participant's randomized group assignment to SVL  
688           or BFL spectacles.

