  - 689           3. The participant will return for a Failure Confirmation Visit (section 3.6) in 2  
690           months (window: 4 to 12 weeks).

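### Footnote f to the section 3.1 visit table starts the Failure Confirmation Visit at 12 months, but sections 3.5, 3.5.1 and 3.6 require it for any qualifying failure from 3 months on

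*Protocol*

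**What the plan says.** Footnote f to the section 3.1 visit table gives the trigger as follows: "If a participant meets failure criteria at the 12-month visit or later and needs a change in refractive correction, new spectacles will be prescribed". The child then returns in 4 to 12 weeks to see whether failure is confirmed.

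The row that this footnote annotates sets the target day as "Visit at which failure criteria met and spectacles updated + 60 days", with no earliest visit.

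Section 3.5 defines failure as something that can be met at any follow-up visit from 3 through 36 months. It then routes sites: "If treatment failure occurs, proceed according to whether the participant failed" before the 36-month visit (section 3.5.1) or at it (section 3.5.2).

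Section 3.5.1 covers everyone who fails before the 36-month visit. For the case "The spectacle correction is NOT within tolerance (section 3.12) and needs to be updated", it says "Failure is NOT CONFIRMED at this visit", orders new spectacles of the randomized type, and adds: "The participant will return for a Failure Confirmation Visit (section 3.6) in 2" months.

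Section 3.6 says that these visits follow suspected failures that "occurred for participants who were found to need a change in spectacles at that time". It adds that a required visit may not be missed, whatever its timing.

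**The concern.** The Failure Confirmation Visit separates a true treatment failure from a poor result caused by an outdated prescription. Section 7.6 times the primary event at the visit where failure is confirmed, and censors a child who is lost before confirmation. The rule for who needs confirmation is therefore part of how the primary endpoint is ascertained.

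The footnote sits in the visit table that sites use for scheduling. A site relying on it at 3, 6 or 9 months could conclude that no confirmation is needed, record the failure as final and prescribe bifocals to a child in the single-vision group. Under section 3.5.1 the same child would receive updated single-vision spectacles and be retested about two months later. The event could be dated too early, or counted when the retest would not have confirmed it, and randomized treatment would end without the required check. The sensitivity analyses in section 7.6.1 would not pick this up. The one that deals with confirmation concerns suspected failures lost before the retest, not failures accepted without one.

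**Working it through.** For the main point there is no figure to reproduce, so the check compares the places that state or bear on the trigger.

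| Place in the protocol | When failure or confirmation applies |
|---|---|
| 3.1, footnote f | 12-month visit onward |
| 3.1, Failure Confirmation row | any visit where failure is met and spectacles are updated |
| 3.5 | failure can be met from 3 to 36 months inclusive |
| 3.5.1 | everyone failing before 36 months whose spectacles are out of tolerance |
| 3.6 | suspected failures needing a spectacle change; no earliest visit |

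Sections 3.5.1 and 3.6 do not print a 3-month start themselves. It comes from section 3.5, which defines the failures on which they act.

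**Visits affected.** Failure is assessed at 3, 6, 9, 12, 18, 24, 30 and 36 months, which is 8 visits. Those before 12 months are 3, 6 and 9, so 3 of 8 are inside the rule but outside the footnote.

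**Can the trigger arise that early?** Yes. Routine cycloplegic refraction in follow-up is at 12, 24 and 30 months, which might suggest a reason for a 12-month start. But section 3.3 item 8 and the schedule of visits also require refraction at any other visit where failure is met. An out-of-tolerance correction can therefore be found at 3, 6 or 9 months.

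**Target windows in the same table.**

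- Failure Confirmation row: day 60 ± 4 weeks is 60 − 28 = 32 to 60 + 28 = 88. The table prints 46 to 88. The lower limit is 60 − 14 = 46, which is a 2-week margin. The other two rows set at 60 days (38-month and Post-failure visits) print 32 to 88 for the same ± 4 weeks.
- 36-month row: day 1096 ± 2 weeks is 1082 to 1110, and ± 4 weeks is 1068 to 1124. The table prints 1068 to 1124 but labels it ± 2 weeks.
- The allowable windows (30 days to open end; 1005 to 1278 days) do not depend on either slip.

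**The case against.** The best reply is that the operative text already settles the matter. The footnote says *if*, not *only if*, and gives no instruction for failures at 3, 6 or 9 months. Section 3.5 sends each failure to 3.5.1 or 3.5.2, section 3.5.1 sets the confirmed and not-confirmed branches side by side, and section 3.6 forbids skipping a required visit. To go wrong, a site would have to read a meaning into the footnote's silence and pass over the section to which it was sent. Early updates may also be uncommon, because enrollment requires a cycloplegic refraction within the previous 3 months and section 2.8 then prescribes full correction.

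All of this stands, and it keeps the point small. It does not make the footnote right: nothing in the protocol explains or supports a 12-month start, and the row it annotates contradicts it.

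A reader might infer that the protocol contains two competing procedures, so that failures before 12 months are confirmed automatically. The documents do not support that, because the footnote never says what happens to those failures. A reader might also try to count the children affected from the planning failure rates of 5% and 15% in section 7.3. Those are 36-month figures. The protocol gives neither the timing of failures nor the share needing new spectacles, so any count would rest on invented inputs. Nor do the window misprints invalidate any visit.

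**Conclusion.** Footnote f states the wrong trigger for the Failure Confirmation Visit and wrongly leaves out the 3-, 6- and 9-month visits. The correct rule is clear from sections 3.5, 3.5.1 and 3.6, which agree with each other. The exposure is confined to children who fail at one of those three visits, need a spectacle update, and attend a site that relies on the footnote over section 3.5.1. Their number cannot be derived from the protocol, and no effect on the hazard ratio, the difference in failure probability or power can be shown. The matter is minor but worth correcting, because it concerns whether and when a primary event is counted. The two target-window slips are typographical.

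**What to change.** In footnote f, delete the words restricting the trigger to the 12-month visit and later, or replace them with: at any visit from 3 to 36 months. Sections 3.5.1, 3.6 and 7.6 need no change.

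In the same edit, print 32 to 88 days as the target window for the Failure Confirmation Visit. Make the 36-month target window agree with its label: either ± 4 weeks with 1068 to 1124 days, or ± 2 weeks with 1082 to 1110 days.

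The cost is one phrase, two table entries and a short memo to sites. No visit, procedure or analysis is added.
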